VERNACULAR 
Clinical Study
CLINICAL STUDY PROTOCOL

Title: The BARD® VENOVO™ Venous Stent Study – A Prospective, Non-Randomized, Multi-Center, Single-Arm Study of the Treatment of Iliofemoral Occlusive Disease – an Assessment for Effectiveness and Safety (VERNACULAR)

Protocol Number: BPV-14-007

Study Type: Investigational Device Exemption (IDE)

Date: January 31, 2018

Version: Version 2.0

Study Device: VENOVO™ Venous Stent System

[figure not shown]
Sponsor: Bard Peripheral Vascular, Inc.
[name]
[name]

Sponsor – [name], Director, Clinical Affairs

3/13/18

Date

Lead Principal Investigator – [name]

03/02/18

Date

European Co-Principal Investigator – [name]

03/03/18

Date

BARD | PERIPHERAL
VASCULAR

This document contains information that is the confidential and proprietary property of Bard Peripheral Vascular, Inc. or its affiliates. Neither this document nor the information herein may be reproduced, used, or disclosed to or for the benefit of any third party without the prior consent of Bard Peripheral Vascular, Inc.
Shred to dispose of document.

NCT02655887

*NCT number added post-approval as per CT.gov requirement

Clinical Protocol Summary

Title:	The BARD [®] VENOVO [™] Venous Stent Study - A Prospective, Non-Randomized, Multi-Center, Single-Arm Study of the Treatment of Iliofemoral Occlusive Disease – an Assessment for Effectiveness and Safety (VERNACULAR)																																																																			
Sponsor:	Bard Peripheral Vascular, Inc. (“Bard”) [name]																																																																			
Objectives:	The objective of this study is to assess the safety and effectiveness of the VENOVO [™] Venous Stent for the treatment of symptomatic iliofemoral venous outflow obstruction. This would include Acute or Chronic Deep Vein Thrombosis (DVT), May-Thurner Syndrome, or any combination of the above.																																																																			
Design:	
This is a prospective, multi-center, non-randomized, single-arm clinical study of the VENOVO[™] Venous Stent for the treatment of symptomatic iliofemoral venous outflow obstruction. Safety and effectiveness measures of subjects receiving the VENOVO[™] Venous Stent will be compared to a Performance Goal (PG) derived from published literature.
 
The study will be conducted at a maximum of 35 investigational sites (“sites”) in the United States, and Europe and Australia/New Zealand.
 
Clinical follow-up for all treated subjects will be performed at hospital discharge, 30-days, and 6-, 12-, 24-, and 36-months post-index procedure.
																																																																			
Devices:	
The VENOVO[™] Venous Stent is comprised of a self-expanding nitinol (nickel-titanium) alloy. The diameter of the flared ends is approximately 3 mm larger than the diameter of the nominal stent body and contains radiopaque tantalum markers.
 
Size Matrix:
 
  
 Stent Diameter (mm)	Delivery System Profile	Stent Length (mm)	
 
 40	60	80	100	120	140	160	
   
 10	8 Fr								
 
 12								
 
 14	9 Fr								
 
 16	10 Fr								
 
 18								
 
 20								
  
	Stent Diameter (mm)	Delivery System Profile	Stent Length (mm)							40	60	80	100	120	140	160	10	8 Fr								12								14	9 Fr								16	10 Fr								18								20							
Stent Diameter (mm)	Delivery System Profile			Stent Length (mm)																																																																
		40	60	80	100	120	140	160																																																												
10	8 Fr																																																																			
12																																																																				
14	9 Fr																																																																			
16	10 Fr																																																																			
18																																																																				
20																																																																				
Enrollment:	
Bard plans for enrollment to continue until a maximum of one-hundred seventy (170) subjects are treated with the VENOVO[™] Venous Stent which is an estimated three hundred forty (340) consecutive subjects in a non-randomized fashion.
 
Subjects will be considered enrolled in the study at the time the informed consent document is signed (an estimated 340 subjects). After the subject has met all eligibility criteria and the VENOVO[™] Venous Stent catheter
																																																																			

	is introduced (i.e. delivery system enters the subject’s body), the subject will enter the primary analysis population (up to 170 subjects).
Investigational Sites:	Up to thirty-five (35) sites will be utilized for this study throughout the United States (U.S.), Europe, and Australia/New Zealand.
Study Population:	Subjects will be males or non-pregnant females, at least 18 years of age, with symptomatic iliofemoral venous outflow obstruction and an expected lifespan sufficient to allow for completion of all study procedures.
Eligibility Criteria:	
Inclusion Criteria
 
 1. The subject provides written informed consent using an Informed Consent Form (ICF) that is reviewed and approved by the Ethics Committee (EC) / Institutional Review Board (IRB) for the site. 2. Subject agrees to comply with the protocol-mandated follow-up procedures and visits. 3. The subject is a male or non-pregnant female ≥ 18 years old with an expected lifespan sufficient to allow for completion of all study procedures. Female subjects of childbearing potential must have a negative pregnancy test (urine or blood) within 14 days prior to the index procedure. 4. The subject has symptomatic (non-malignant) venous outflow obstruction in iliofemoral “venous segments” (unilateral obstruction of the common femoral vein, external iliac vein, common iliac vein, or any combination thereof) of $\geq 50\%$ as determined by catheter contrast venography. 5. The subject has symptomatic venous outflow obstruction (non-malignant) in iliofemoral venous segments with a Clinical-Etiology-Anatomic-Pathophysiologic Score CEAP “C” ≥ 3 or a Venous Clinical Severity Score VCSS pain score of ≥ 2. 6. The subject is able and willing to comply with any required medication regimen. 7. The reference vessel diameter(s) (RVD) is (are) between 7mm and 19mm as determined by the Investigator’s visual estimate. 
Exclusion Criteria
 
 1. The subject is unable or unwilling to provide written informed consent, or is unable or unwilling to conform to the study protocol follow-up procedures and visits. 2. The subject is or plans to become pregnant during the study. 3. The subject has contralateral disease of the common femoral vein, external iliac vein, common iliac vein, or any combination thereof and does not meet the venous outflow obstruction requirement as determined by the treating Investigator or the target vessel has a malignant obstruction. 4. The subject is asymptomatic, has a CEAP “C” <3, or a VCSS pain score of <2. 5. The subject has a venous obstruction that extends into the inferior vena cava (IVC) or below the level of the lesser trochanter. 6. The subject has a known uncorrectable bleeding diathesis or active coagulopathy.

	
 7. The subject has a known allergy or sensitivity to Nickel or Titanium or has intolerance to antiplatelet, anticoagulant or thrombolytic medications required per the protocol 8. The subject has a known allergy or sensitivity to contrast media, which cannot be adequately pre-medicated. 9. The subject has any planned surgical interventions (other than pre-stenting procedures of thrombolysis, thrombectomy, and/or vena cava filter placement in patients at high risk for pulmonary embolism) within 30 days prior to, or within 30 days after the planned study procedure. 10. The subject has a lesion(s) or occlusion(s) which cannot be traversed with a guidewire. 11. The subject has had prior stenting in the target vessel. 12. The subject has iliofemoral venous segments unsuitable for treatment with available sizes of study devices. 13. The subject has another medical condition, which, in the opinion of the Investigator, may cause him/her to be non-compliant with the protocol, confound the data interpretation, or is associated with a life expectancy insufficient to allow for the completion of study procedures and follow-up. 14. The subject is currently participating in an investigational drug, biologic, or another device study for which the investigational treatment has not ended. Studies requiring extended follow-up for products that are now commercially available are not considered investigational studies. 15. The subject is currently on dialysis or has a serum creatinine ≥ 2.5 mg/dl.

Procedures:
	
All subjects will undergo a clinical evaluation at baseline/screening (prior to index procedure); treated subjects will undergo additional clinical evaluations prior to hospital discharge, at 30-days and 6-, 12-, 24- and 36-months post-index procedure.


Primary Endpoint:
	
Safety: Freedom from Major Adverse Events (MAEs) through 30 days Defined as the following:
 
 • Device and/or procedure related death • Major amputation of target limb • Pulmonary Embolism which is clinically important (symptomatic with chest pain, hemoptysis, dyspnea, hypoxia, etc.) • Target Vessel Revascularization (TVR) • Vascular injury requiring surgical/endovascular intervention • Embolization/migration of stent • Device or procedure related acute DVT involving the treated limb 
Efficacy: Primary Patency rate at 12 months defined as Freedom from TVR; freedom from thrombus occlusion and stenosis $> 50\%$ as measured by DUS. Note: Venography will be used only if investigator cannot successfully measure endpoint by DUS or if the investigator deems there is clinical need to perform invasive venography.

Secondary Endpoints:
	
 - Evaluation of VCSS Scores at 30 days, 6, 12, 24, and 36 months - Quality of Life Questionnaire (QOL) at 30 days, 6, 12, 24, and 36 months - Evaluation of CEAP Scores at 30 days, 6, 12, 24, and 36 months - Acute Procedure Success - Lesion Success - Acute Technical Success - Freedom From Target Lesion Revascularization (TLR) at 30 days, 6, 24, 36 months - Freedom From Target Vessel Revascularization (TVR) at 30 days, 6, 24, 36 months - Primary Patency at 24, 36 months - X-ray analysis for stent fracture at 12, 24, and 36 months

Lead Principal Investigator:
	
[name] Thelma and Henry Doelger Professor (III) Department of Cardiothoracic Surgery Stanford University School of Medicine Falk Cardiovascular Research Center [name] [contact] [contact] Email: [contact]

European Co-Principal Investigator
	
[name] University Hospital Galway [name] [contact] Email: [contact]

Venographic Core Lab:
	
[name] Yale Cardiovascular Research Group [name] [contact]

Duplex Ultrasound Core Lab:
	
[name], MSc, MHA,FSVM, RPVI Vascular Ultrasound Core Lab Massachusetts General Hospital [name] [contact]

Please refer to Site Contacts List for all Sponsor, Investigator, and Vendor contact information.

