1.3.2. Analysis of the VCSS Pain Assessment

The first Secondary Objective is to evaluate whether the *VCSS Pain Assessment* of the BVS improves between the baseline classification and the follow-up classifications at 6, 12, 24, and 36 months. The

emphasis will be on the change between baseline and 12 months, since that is the time of the endpoint for the Primary Efficacy Objective. The four classes of VCSS for pain have been discussed previously in this Investigational Plan. (The VCSS includes clinical signs and symptoms other than pain, but this objective focuses only on pain.)

The objective is to demonstrate that the distribution of classifications improves from baseline to each follow-up time, especially at 12 months. This requires testing the null hypothesis (H_0) that the distribution at the 12-month follow-up ($D_{BVS@12M}$) remains unchanged compared to baseline ($D_{BVS@BL}$) against the alternative hypothesis (H_a) that the distribution shifts toward lower (less pain) classes:

$$H_0: D_{BVS@12M} \geq D_{BVS@BL} \quad \text{vs} \quad H_a: D_{BVS@12M} < D_{BVS@BL}$$

The endpoint for each study subject is the VCSS pain class at baseline and at each follow-up time (6, 12, 24, and 36 months).

Paired mean difference of the 12-month follow-up and baseline pain score and 95% CI will be presented. If the mean difference < 0 and the two-sided p-value from the paired t-test is deemed significant based on the appropriate α -level as described above, this will indicate success for this endpoint.

In addition, the VCSS pain class at each time point will be summarized descriptively..

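### VCSS pain of 2 or more is an entry route, and the score that qualifies a subject appears also to be the baseline of the uncontrolled pain test, so regression to the mean biases the change towards improvement

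*Combined protocol and SAP*

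**What the plan says.** Entry (Clinical Protocol Summary, Eligibility Criteria). Inclusion criterion 5 requires CEAP C of at least 3 "or a Venous Clinical Severity Score VCSS pain score of ≥ 2", so pain is one of two routes. Exclusion criterion 4 removes a subject who is asymptomatic, has CEAP C below 3, "or a VCSS pain score of <2". Read literally, either shortfall excludes, and every treated subject must then have pain of at least 2.

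Baseline (Clinical Protocol Summary, Procedures). One pre-treatment evaluation is described: "All subjects will undergo a clinical evaluation at baseline/screening (prior to index procedure"). No second pre-procedure pain rating is mentioned.

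Design (Clinical Protocol Summary, Design). "This is a prospective, multi-center, non-randomized, single-arm clinical study".

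Analysis (SAP 1.3.2). "Paired mean difference of the 12-month follow-up and baseline pain score and 95% CI will be presented". Success is declared on this rule: "If the mean difference < 0 and the two-sided p-value from the paired t-test is deemed significant", at the level set by the Hochberg procedure in SAP 1.3.1. The comparison is with zero change. Pain is one of two secondary endpoints with a hypothesis test, and both are tested only after the two co-primary hypotheses pass.

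**The concern.** A pain score fluctuates from one rating to the next. If a subject enters because a reading was high, that reading is on average above the subject's usual level, and a later reading tends to be lower even if nothing has changed. If the same reading is the analysis baseline, the fall is counted as improvement. There is no control arm to show how much fall to expect, and 1.3.2 sets no performance goal or minimum change for pain, whereas the co-primary endpoints must beat goals of 74% and 89%.

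At stake are the estimate, interval and success claim for one of only two tested secondary endpoints. The Hochberg procedure presumes valid p-values and cannot correct a biased baseline.

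**Working it through.** **1. The plan's own figures.** The plan gives no SD, effect size or power for the pain test. The only figure to carry over is the 138 evaluable subjects (SAP 1.4). It reproduces: with an exact one-sided binomial test of 70% against 80%, success needs at least 106 of 138, with actual alpha 0.0466 and power 0.8512.

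**2. Nominal error.** A two-sided 0.05 test that also requires a negative mean has a false-success rate of 0.05/2 = 2.5%.

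**3. Drift that matters.** The chance of success reaches about 50% when the drift equals t(0.975, 137) × SD/√138, with t = 1.977 and √138 = 11.75.
- SD of change 0.7 (assumed): 1.977 × 0.7/11.75 = 0.12 points.
- SD of change 1.0 (assumed): 1.977 × 1.0/11.75 = 0.17 points.

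**4. Model for the drift (all inputs assumed; none is in the documents).** Latent pain in screened patients is normal with mean 1.5 to 2.0 and SD 0.9, and is rounded and clipped to 0–3. Test-retest correlation is 0.6 to 0.9. There is no true change. CEAP class is independent of pain. Selection acts on the first reading; change is the second minus the first.

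Subjects with C of at least 3 under the either/or rule are not selected on pain and have zero expected drift. Hence:

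drift = (share admitted on pain alone) × (drift among subjects with pain of 2 or more)

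With q the share of screened patients with C of at least 3, and a the share with pain of 2 or more, the pain-alone share is (1 − q)a / [q + (1 − q)a].

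**5. Worked case at the unfavourable end** (mean 1.5, correlation 0.6). Rounding puts the cut at 1.5, so a = 0.50. The model gives a drift of 0.36 among subjects with pain of 2 or more. The SD of change in the model is about 0.78 if pain is mandatory and 0.85 to 0.86 under the either/or rule. Chance of success ≈ Φ(drift × 11.75/SD − 1.98).
- Mandatory: 0.36 × 11.75/0.78 = 5.4, giving over 99%.
- q = 50%: share 0.25/0.75 = 0.333; drift 0.333 × 0.36 = 0.12; Φ(1.66 − 1.98) ≈ 38%.
- q = 70%: share 0.15/0.85 = 0.176; drift 0.064; Φ(0.87 − 1.98) ≈ 14%.
- q = 90%: share 0.05/0.95 = 0.053; drift 0.019; Φ(0.26 − 1.98) ≈ 4%.

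**6. Results over the assumed range** (n = 138, two-sided 0.05; simulation error is about one percentage point).

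| Entry rule applied | Chance of false success |
|---|---|
| Pain of 2 or more mandatory (drift 0.09 to 0.36) | about 53% to over 99% |
| Either/or, 50% with C of at least 3 | 13% to 38% |
| Either/or, 70% | 7% to 14% |
| Either/or, 90% | about 4% |

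If Hochberg requires 0.025, the first three rows fall to about 41% to over 99%, 8% to 28%, and 4% to 9%.

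**7. Sensitivity to the pain distribution.** With three other assumed class distributions and correlations of 0.5 to 0.9, the chance is 45% to over 99% if pain is mandatory. Under the either/or rule it is 11% to 49% at 50% with C of at least 3, 5% to 9% at 80%, and 3% to 5% at 90–95%.

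**8. Check of the remedy.** In the same model, a baseline rating not used for eligibility returns the rate to about 2.5%, provided the rating errors are independent.

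**The case against.** The strongest objection is that the central link is inferred. No sentence says that the eligibility score is the analysis baseline. SAP 1.3.2 refers only to a baseline classification and points elsewhere for the scale: "The four classes of VCSS for pain have been discussed previously in this Investigational Plan". The supplied text does not include that discussion or a visit schedule, so a separate pre-procedure rating cannot be ruled out. This stands: the claim is that the qualifying score appears to be the baseline, because no other is described.

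A reader might infer that pain of 2 or more is simply the entry threshold, and that the pain test is therefore bound to succeed without benefit. The documents do not support this. Inclusion criterion 5 has a CEAP route, subjects entering that way are not selected on pain, and the artefact is near nominal when about 90% have C of at least 3. The high figures need exclusion criterion 4 to be applied literally.

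A reader might also infer that the trial's main conclusion is in doubt. It is not: pain is tested only after both co-primary endpoints succeed. That gating does not protect the pain claim itself, since the test runs exactly when the device has passed.

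Finally, regression to the mean is only one part of what a single-arm change cannot separate from a device effect; natural course and co-treatment remain. This also stands, and it limits what any choice of baseline can achieve.

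**Conclusion.** The concern holds with these limits. The direction of the bias follows if the qualifying score is the baseline, pain ratings repeat imperfectly, and some subjects are admitted because of their pain score. The size cannot be determined from the documents, which give no pain distribution, retest correlation, SD or CEAP mix. It depends mostly on which criterion governed entry: under the assumptions above, false success ranges from near nominal (either/or rule, most subjects with C of at least 3) to almost certain (pain mandatory). If the true improvement is large, the test conclusion would not change, but the mean and interval would still be shifted by the drift. The harm is confined to the secondary pain claim.

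**What to change.** 1. Reconcile inclusion criterion 5 with exclusion criterion 4, and record which rule was applied to the subjects already enrolled.
2. In SAP 1.3.2, state that the baseline is a pre-treatment VCSS pain rating not used for eligibility, and use it for the paired difference, confidence interval and test. This is one repeated 0–3 item, taken before the index procedure and before any pre-stenting treatment (exclusion criterion 9 allows for thrombolysis or thrombectomy, which could otherwise already affect the score).
3. For subjects already enrolled without such a rating, keep the all-subject test and add a pre-specified sensitivity analysis of the paired change by entry route (C of at least 3 versus pain only). It is informative only if the either/or rule was applied; under a literal exclusion criterion 4, every C-of-at-least-3 subject was also selected on pain. It should not replace the main test, because it would set aside the subjects for whom a pain outcome matters most.
4. Do not attribute the whole pain change to the device.

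Cost: one extra item, SAP wording, and probably a somewhat smaller reported improvement. If the two pre-treatment ratings are close in time they may share the same flare, and the bias is then only partly removed.

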1 STATISTICAL ANALYSIS PLAN

1.1. Analysis Populations

Several populations of patients enrolled into the trial need to be defined.

The intent-to-treat (ITT) population consists of those subjects who have signed the Informed Consent Form and had the VENOVO™ Venous Stent catheter introduced (i.e., delivery system enters the subject's body).

Subjects who do not receive the study implant (section 5.2.2), but in whom the VENOVO™ Venous Stent catheter was introduced will be included in the ITT population. Subjects who need more than two (2) VENOVO™ Venous Stents (section 5.2.3) or undergo other treatment modalities (section 5.2.4) will be included in the ITT population.

A per-protocol (PP) population may be created if there are subjects who have any major protocol deviations. Major Protocol Deviations are defined as those that occur to protect the life or physical well-being of a subject in an emergency, or those that may affect the scientific soundness of the study, or the rights, safety or welfare of human subjects. The PP population will consist of any subjects in the ITT population who receive at least one stent and do not have any major protocol deviations, including deviations of study eligibility criteria. Subjects who need more than two (2) VENOVO™ Venous Stents, require placement of a commercially-available stent (section 5.2.3), or undergo other treatment modalities (section 5.2.4) will be excluded from the PP population.

All effectiveness and safety analyses including the primary analysis will be primarily based on the ITT population. A PP analysis may also be performed for the primary endpoint. It will only serve as a sensitivity analysis for the primary analysis which is based on the ITT population.

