1.2.1. Primary Efficacy Endpoint

The Primary Efficacy endpoint is the *primary patency* of the VENOVO™ Venous Stent (BVS) at 12 months post index procedure, which need to be better than the Performance Goal (PG) (74%) developed from the patency of other marketed stents at 12 months (see section 6.4 sample size consideration for the derivation of the PG).

The primary efficacy endpoint will be evaluated by the following hypothesis:

- H₀: The primary patency rate at 12 months post index procedure from the overall VENOVO™ Venous Stent (BVS) patients (PTS and NIVL combined) is at most as good as that of the PG;
H_a: The primary patency rate at 12 months post index procedure from the overall VENOVO™ Venous Stent (BVS) patients (PTS and NIVL combined) is better than that of the PG;

$$H_0: 0.45 \times \pi_{NIVL} + 0.55 \times \pi_{PTS} \leq PP_{PG} \text{ v.s } H_a: 0.45 \times \pi_{NIVL} + 0.55 \times \pi_{PTS} > PP_{PG}$$

Where π_{PTS} is the true primary patency rate at 12-month post index procedure for PTS patients, π_{NIVL} is the true primary patency rate at 12-month post index procedure for NIVL patients, and $PP_{PG}=74\%$. The test statistics can be formulated as:

$$Z = \frac{0.45 \times p_{NIVL} + 0.55 \times p_{PTS} - 0.74}{\sqrt{\frac{(0.45)^2 \times PG_{NIVL}(1 - PG_{NIVL})}{n_{NIVL}} + \frac{(0.55)^2 \times PG_{PTS}(1 - PG_{PTS})}{n_{PTS}}}}$$

Where p_{PTS} and p_{NIVL} are observed primary patency rate at 12-month post-index procedure for PTS and NIVL patients, respectively. PG_{PTS} ($=77\%-10\%=67\%$) and PG_{NIVL} ($=93\%-10\%=83\%$) are expected value for PTS and NIVL patients under the null; n_{PTS} and n_{NIVL} are the number of PTS and NIVL patients in the analysis. A one-sided p-value will be calculated using a normal distribution. The study device will be considered to have achieved the primary efficacy objective if the one-sided p-value is less than 0.05.

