1.2.3. Handling of Missing Data

Study endpoints may be missing due to withdrawal of consent, investigator's decision to terminate, lost to follow-up and death. As long as the missing data is unrelated to the study intervention and the observed and unobserved data, limiting the analysis to those subjects who contribute endpoints produces unbiased estimates of the event rates.

The *reason* for missing data in any subject will be reported. If there is any indication that missing data is related to the study intervention, a worst-case analysis may be performed in addition to the standard analysis. In a worst-case analysis, a failure of effectiveness or safety will be assumed to have occurred at the time the subject was censored.

In addition, regardless of whether missing data are related to the study intervention, a tipping-point analysis will be performed, in which assumptions about missing data are varied from worst-case to best-case to examine at what point the missing data would alter the results of the analysis.

Multiple imputation will also be explored as another method to handle missing data.

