1.4. Sample Size Consideration

Primary Efficacy Endpoints:

Table 6.3-1 shows the possible combinations of proportions of patients that could be enrolled in the study along with the weighted mean primary patency (PP) and the sample size required for 85% power against the PG (PP_{PG}).

Bard has chosen the sample size for the trial required for 85% power when the proportion of NIVL patients with endpoints is 20% and the proportion of PTS patients is 80%. This is the company's best guess for the actual enrollment. The estimate from the literature of the PP is 80% (used as the alternative proportion in the sample size estimate) and the PP_{PG} is 70% (used as the null proportion). The sample size is 138 patients. (This row is highlighted in yellow in Table 1.3-1.). With 45:55 split of the sample size, the PP_{PG} becomes 74%. As indicated in Table 6.3-1, the sample size required for 85% power will be between 121 and 125, which is less than planned sample size 138. In other words, with the same sample size as planned, >85% power can be achieved.

All sample size estimates in Table 1.3-1 were made with PASS 12 (Hintze, J. (2013). PASS 12. NCSS, LLC. Kaysville, Utah, USA. www.ncss.com) using the Fisher's Exact Binomial test for one proportion.

Note that the sample size of 138 patients is the number of evaluable patients. Up to 170 patients may be enrolled, depending on the losses-to-follow-up, deaths, and study withdrawals. Bard further estimates that approximately 50% of consented subjects will not meet the eligibility criteria (i.e., will

be Screen Failures), and therefore will not be enrolled in the study. The estimated consented population will therefore be 340 ($170/.5 = 340$).

Table 1.3 -1. Estimates of the Sample Size Based on the Proportions of NIVL and PTS Subjects in the Clinical Trial

NIVL %	PTS %	Weighted Mean PP	α	Performance Goal (PP _{PG})	Sample Size of BVS for 85% Power
5%	95%	77.9%	5%	68%	146
10%	90%	78.7%	5%	69%	140
20%	80%	80.4%	5%	70%	138
30%	70%	82.0%	5%	72%	132
40%	60%	83.6%	5%	74%	125
50%	50%	85.2%	5%	75%	121
60%	40%	86.9%	5%	77%	112

Primary Safety Endpoint:

The freedom-from-MAE rate estimated from the literature was 99%, which was used as the alternative proportion. The null proportion was the M_{PG} of 89%. With 42 BVS subjects, the study will have 85% power to detect a difference, and with 138 BVS subjects, the study power will be over 99%.

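### The primary ITT set keeps subjects in whom no study stent was implanted, but the available SAP text gives them no patency outcome, so delivery failures can drop out of the efficacy test

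*Combined protocol and SAP*

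**What the plan says.** Section 1.1 defines ITT by consent plus introduction of the delivery catheter, and bases the primary analysis on ITT. It foresees "Subjects who do not receive the study implant (section 5.2.2") and rules that those in whom the "catheter was introduced will be included in the ITT population". Only the per-protocol set requires at least one stent.

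Section 1.2.1 defines the efficacy endpoint as primary patency of the VENOVO stent at 12 months. The denominators of the Z statistic "are the number of PTS and NIVL patients in the analysis"; they are not said to be all ITT subjects. The decision rule is: "The study device will be considered to have achieved the primary efficacy objective if the one-sided p-value is less than 0.05".

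Section 1.2.3 lists four causes of missing endpoints: consent withdrawal, investigator termination, loss to follow-up and death. On condition that missingness is unrelated to the intervention and to the data, it says that "limiting the analysis to those subjects who contribute endpoints produces unbiased estimates of the event rates". If missingness appears related to the intervention, a worst-case analysis is optional and comes on top of the standard one. A tipping-point analysis is mandatory, and multiple imputation will be explored.

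The Clinical Protocol Summary (Procedures) states post-procedure visits for treated subjects. Its Primary Endpoint entry defines patency as freedom from TVR, thrombotic occlusion and stenosis above 50% on duplex ultrasound.

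**The concern.** A subject whose stent could not be delivered belongs to the primary analysis set, but the available text assigns that subject no outcome. Two readings are open.

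- **The subject has no endpoint and is left out.** Where non-implantation is a delivery failure, it is related to the intervention, so the SAP's own condition for an unbiased complete-case estimate is not met. Section 1.2.3 nevertheless leaves that estimate as the standard analysis.
- **The treated vein is scanned and scored.** A vein kept open by other means could then count as a success of a device that was never implanted.

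Under either reading a device failure escapes being counted as one. At stake is the pass/fail result of a single-arm trial against a fixed goal, where no control arm shares the bias.

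**Working it through.** **1. The plan's own figure.** Section 1.4 says "Bard has chosen the sample size for the trial required for 85% power" at a 20:80 NIVL:PTS mix. It adds "The estimate from the literature of the PP is 80% (used as the alternative proportion in the sample size estimate"), and the performance goal "is 70% (used as the null proportion"). For a one-sided exact binomial test at 0.05, the smallest n with at least 85% power is 138: reject at 106 or more patent, exact alpha 0.0466, power 85.1%. The stated 138 reproduces. It counts evaluable patients, and the attrition reasons given for enrolling up to 170 do not include non-implantation.

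**2. Threshold of the primary test.** Inputs from section 1.2.1: weights 0.45 and 0.55, goal 74%, null rates 83% (NIVL) and 67% (PTS). A 45:55 split of 138 gives 62 and 76.

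- SE = sqrt(0.45² × 0.83 × 0.17/62 + 0.55² × 0.67 × 0.33/76) = 0.0366
- Cut-off = 0.74 + 1.645 × 0.0366 = 80.0%
- One subject moves the estimate by about 0.72 points (0.45/62 or 0.55/76).

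**3. One subject can decide.** Take 55/62 NIVL and 56/76 PTS patent among implanted subjects. The estimate is 0.45 × 55/62 + 0.55 × 56/76 = 80.4%, Z = 1.76, p = 0.039: pass. Add one non-implant as a failure:

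- in NIVL (55/63): 79.8%, Z = 1.59, p = 0.056: no pass
- in PTS (56/77): 79.9%, Z = 1.62, p = 0.052: no pass

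**4. Chance of passing when true success is at the goal.** Let d be the share of ITT subjects without an implant. The documents give no value, so d = 1% to 5% is an assumption. Non-implants are spread evenly over the strata and dropped, with 138 subjects remaining in the test. The rates are 82.78% and 66.78%, a weighted 73.98%. If all non-implants are failures, the rate among those analysed is the true rate divided by (1 − d). If half would be patent, and true success is counted on that basis, it is (true rate − 0.5d)/(1 − d). Rejection probabilities come from exact enumeration of the two binomials.

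| d | Expected estimate, all failures | Pass, all failures | Pass, half patent |
|---|---|---|---|
| 0 | 74.0% | 4.5% | 4.5% |
| 1% | 74.7% | 6.8% | 5.2% |
| 2% | 75.5% | 9.9% | 5.9% |
| 3% | 76.3% | 14.1% | 6.7% |
| 5% | 77.9% | 26.5% | 8.7% |

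Scaling the rates to exactly 74.0% changes the all-failures column only to 4.6%, 6.8%, 10.0%, 14.2% and 26.7%. Starting instead from 138 ITT subjects and removing whole subjects (2, 3, 4 and 7 of them) gives about 8%, 9%, 13% and 23%. If non-implants are patent at 74%, like everyone else, there is no inflation.

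**5. Power if non-implants are scored as failures.** At 93% and 77% patency in implanted subjects and 138 in the test, both rates are multiplied by (1 − d). Power is 91% at d = 0, then 85%, 78%, 69% and 50% at 1%, 2%, 3% and 5%.

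**The case against.** The strongest objection is that the text is incomplete. Section 1.1 points to 5.2.2 for exactly these subjects, and section 1.3.5 points to 3.2 for the definitions of secondary endpoints. Either might hold a scoring or follow-up rule. This stands, and both must be checked before the SAP is changed.

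Second, a reader might infer that the plan directs these subjects to be dropped. It does not. Section 1.1 includes them in ITT, non-implantation is not among the listed causes of missing data, and the complete-case sentence is conditional. The text permits the exclusion without ordering it. If these subjects are classed as missing, the mandatory tipping-point analysis would show how much they matter, but it does not alter the pass rule.

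Third, a reader might infer that a non-implanted subject cannot have a patency outcome, or that the bias can run only one way. Neither is supported. The components of the endpoint can be read in an unstented vein or one treated otherwise, and the documents do not say why non-implantation occurs. Upward bias follows only so far as these subjects are device failures.

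Fourth, scoring them as not patent is one choice of estimand among several. The goal comes from published patency of other stents, and the available text does not show whether those sources counted non-implants as failures. This is a fair caution. It argues for reporting other scorings alongside, not for leaving the primary score undefined.

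**Conclusion.** The point holds as a gap in the primary analysis rule. The available SAP text keeps non-implanted subjects in the primary set, gives them no outcome, and leaves a complete-case result as the standard analysis even where missingness is related to the intervention. It is more than missing detail, because a result near the 80.0% threshold can turn on one or two such subjects.

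The size is uncertain. The increase from 4.5% to as much as 26.5% is the unfavourable end: it needs a 5% non-implant rate, every non-implant a true failure, all of them dropped, and true success at the goal. At 1% to 2% the figure is 6.8% to 9.9%, and if half would be patent it stays at about 5% to 9% over the whole assumed range. The conclusion lapses if 3.2 or 5.2.2 already fixes the score; a cross-reference would then be enough.

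**What to change.** Check sections 3.2 and 5.2.2 first. If they hold no rule, add to 1.2.1 and 1.2.3: *ITT subjects in whom no VENOVO stent is implanted are counted as not patent in the primary efficacy test, within their PTS or NIVL stratum, and are not treated as missing.* Report two sensitivity analyses: implanted subjects only, and vein patency as observed whatever treatment was given. Settle the rule before outcomes are known.

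The drafting cost is one sentence. The statistical cost is a less favourable estimate and lower power if non-implants occur: from about 91% to 85% at 1% and 78% at 2%, on the assumptions in step 5. With no non-implants it costs nothing. The sponsor should state the non-implant rate it expects, and consider whether 138 evaluable subjects still suffice at that rate.
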